5.2 Convalescent Plasma Group

Patients randomized to the active treatment arm will receive a single dose of 1 unit (200-399 ml) of convalescent plasma infused intravenously per site institutional policy governing blood product transfusions. Convalescent plasma used in this trial will be ABO compatible with the participant's blood type. The convalescent plasma will be supplied to enrolling sites for the trial. Quantitative SARS-CoV-2 antibody testing will be completed at Vanderbilt University Medical Center on convalescent plasma used in the trial. Plasma that is believed to be neutralizing will be used in this trial and will be prioritized based on neutralizing capabilities. Only plasma that contains anti-SARS-CoV-2 antibodies at a level above the threshold for neutralization will be used in the trial.

5.3 Control Group

Participants randomized to the control group will receive a single 250 ml dose of lactated Ringer's containing multivitamins intravenously. This placebo solution will be mixed by local site pharmacies. It is stable under refrigeration for up to 24 hours. This solution is similar in appearance to plasma and is used to help blind patients, families, and study personnel to treatment assignment.

5.4 Co-interventions

Use of open label convalescent plasma in the first 15 days of the study is strongly discouraged and will be tracked as protocol deviations. All other treatment decisions will be made by treating clinicians without influence from the protocol. Administration of other antiviral medications will be allowed. The decision to administer other antiviral medications will be made by treating clinicians and will be recorded in the case report form. The decision to administer immunomodulating medications, including corticosteroids, will be made by treating clinicians and will be recorded in the case report form.

5.5 On-Study Monitoring

All patients enrolled in the study will be initially hospitalized and will therefore receive monitoring as a part of routine clinical care, including monitoring by their physicians, nurses, respiratory therapists, and ancillary staff.

In addition to routine clinical monitoring, enrolled patients will be monitored per site institutional transfusion policy before, during and following the study infusion. If the patient develops abnormal vital signs during the infusion, the infusion will be held, and the patient will undergo evaluation for a transfusion reaction before the infusion can be restarted. At any point, if a clinical team member has a concern about a potential transfusion reaction, he/she will report that concern to the blood bank or as per institutional policy.

5.6 Criteria for Stopping Study Infusion

Infusion of study treatment will be halted if any of the following manifestations of transfusion reaction develop fever, rash, diffuse itching, acute increase in heart rate by greater than 20 beats per minute. If any of these symptoms develop, the patient will be evaluated by a clinician or study team member. Study treatment will be held until resolution of the symptoms. Study treatment will be restarted one time, but if symptoms recur, study treatment will be discontinued and not restarted. If the patient has recurrent symptoms on restarting study treatment, the blood bank will be notified to evaluate for potential transfusion reaction. If there is significant concern that the symptoms, beyond rash or itching, are secondary to the infusion, then infusion will not be restarted, and the patient will be evaluated for transfusion reaction.

In addition, the infusion will be stopped and not restarted if the patient develops any of the following signs or symptoms of anaphylaxis: hives; pruritus; flushing; swollen lips, tongue or uvula; worsening of shortness of breath; wheezing; stridor; hypoxemia; a decrease in systolic blood pressure to less than 90 mmHg or greater than 30% decrease from baseline or a diastolic drop of greater than 30% from baseline; bradycardia less than 40 beats per minute that is associated with dizziness, nausea or feeling faint; any other symptom or sign which

in the good clinical judgment of the study clinician or supervising provider warrants halting the infusion. For example, the rapid onset of gastrointestinal symptoms, such as nausea, vomiting, diarrhea, and cramps, may be manifestations of anaphylaxis and may warrant an immediate halt prior to meeting full severe adverse event (SAE) criteria.

Any suspected reactions related to study product that result in stopping of study transfusion must be reported as an adverse event.

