12.3 Safety Monitoring

Assuring patient safety is an essential component of this protocol. Each participating investigator has primary responsibility for the safety of the individual participants under his or her care. The investigators will determine daily if any adverse events occur during the period from enrollment through **study day 4,(which is** 72 hours after completion of the study product infusion, or hospital discharge, whichever occurs first, and will determine if adverse events are related to study procedures. Adverse events are not required to be reported to the IRB unless the investigator feels the adverse event **was related** to study infusion or study procedures.

The following adverse events will be collected in the adverse event case report forms:

- Serious adverse events (as defined in protocol section 12.2 of this protocol) that are study related (or of uncertain relationship) or occur within 72 hours of the study infusion
- Non-serious adverse events that are study procedures or of uncertain relationship
- Events leading to permanent discontinuation of study infusion (which, by definition, are study related)

The protocol for reporting adverse events in the trial's electronic data capture system are summarized in Table 4.

Table 4. Protocol for reporting adverse events

Type of Adverse Event	Time for Recording in the EDC
Serious, study related	24 hours
Serious, not study related and within 72 hours of infusion	72 hours
Serious, not study related and after 72 hours following	Recording in the EDC is not required
Not serious, study related	72 hours
Not serious, not study related	Recording in the EDC is not required

Study-specific clinical outcomes (Primary, Secondary and Safety Outcomes and Assessments During the Study), including serious outcomes such as organ failures and death, are systematically recorded in the case report forms and are exempt from adverse event reporting unless the investigator deems the event to be related to the administration of study plasma or the conduct of study procedures (or of uncertain relationship).

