12.4 Medical Monitor

The relationship or attribution of an adverse event to the study therapy will be initially determined by the site investigator and recorded on the appropriate eCRF. Final determination of attribution for safety reporting will be determined by the independent medical monitor. The Medical Monitor may escalate reported events to the DSMB chair as appropriate per the DSMB charter.

The activities of the Medical Monitor will include:

- Being on call for investigators to report and discuss AEs and SAEs
- Reviewing safety data delivered to the DSMB and any safety reports
- Attending DSMB meetings to participate in discussions about safety and AEs
- Participation in discussions about unblinding study team members to study drug allocation to facilitate safe treatment of study participants

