11.5 Transfusion reaction

Patients meeting any of the following within 6 hours of initiation of the study product infusion will be classified as experiencing symptoms consistent with a transfusion reaction:

- New increase in body temperature, defined as temperature >38.0 C (100.4 F) or increase in temperature by >1 C (1.8 F) compared to temperature at the beginning of the infusion

- Decline in oxygen saturation, defined as an absolute drop in SpO₂ by more than 4% or increase in supplemental oxygen to prevent an absolute drop in SpO₂ by more than 4%
- New hives
- New rash (other than hives)
- New itching
- Chest imaging, such as a chest x-ray, demonstrating new or worsening pulmonary edema, pulmonary infiltrates, or effusion
- Clinically diagnosed anaphylaxis

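### Protocol 5.6 puts isolated itching under two incompatible restart rules and does not say which one applies

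*Protocol*

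**What the plan says.** Protocol 5.6 has two operative paragraphs on stopping an infusion.

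The opening paragraph concerns transfusion reactions: "Infusion of study treatment will be halted if any of the following manifestations of transfusion reaction develop fever, rash, diffuse itching", with an acute rise in heart rate as the remaining trigger. A clinician or study team member evaluates the patient. Then: "Study treatment will be held until resolution of the symptoms. Study treatment will be restarted one time". Permanent discontinuation follows if the symptoms come back. The paragraph also has its own route to no restart: "If there is significant concern that the symptoms, beyond rash or itching, are secondary to the infusion, then infusion will not be restarted".

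The second paragraph is introduced as an addition to the first and concerns anaphylaxis: "the infusion will be stopped and not restarted if the patient develops any of the following signs or symptoms of anaphylaxis: hives; pruritus; flushing". The list goes on to respiratory, blood-pressure and heart-rate signs. It ends with a catch-all for any other sign that, in clinical judgment, warrants halting the infusion.

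Two other sections bear on the consequence. Protocol 12.3 collects "Events leading to permanent discontinuation of study infusion (which, by definition, are study related" on the adverse event forms. Protocol 12.4 adds: "Final determination of attribution for safety reporting will be determined by the independent medical monitor".

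**The concern.** Diffuse itching in the opening paragraph and pruritus in the second are the same symptom, and the second paragraph does not qualify it. The actions attached to it cannot both be carried out: one is a pause followed by a restart, the other a permanent stop. Both are worded as requirements.

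This is a bedside safety instruction in a multicentre trial. If it can be read two ways, the same isolated itching could lead to re-exposure at one site and to permanent stopping at another. Neither site would be departing from the text it relied on, and a monitor would have no basis for calling either one a deviation. A smaller consequence is that the relatedness label first given to the event may depend on which paragraph the site followed, because 12.3 ties that label to permanent discontinuation.

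**Working it through.** There is no figure to reproduce, so the check is textual. It applies each paragraph of Protocol 5.6 to a participant whose only sign during the infusion is diffuse itching, then looks for a provision that chooses between the results.

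1. **Opening paragraph.** Diffuse itching is a named trigger and any one trigger is enough, so the infusion is paused. Once the itching clears, one restart follows. The no-restart clause does not catch this patient, because it reaches only symptoms beyond rash or itching. Result: pause, restart once, discontinue on recurrence.

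2. **Second paragraph.** Pruritus is a named item and any one item is enough. It carries no qualifier, so it is at least as broad as diffuse itching. The clinical-judgment wording belongs to the closing catch-all, not to pruritus. Result: stop, no restart.

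3. **Comparison.** The two results are incompatible for this patient.

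4. **Search for a provision that settles it.**
   - Protocol 5.1 and 5.2 leave infusion practice and monitoring to the provider, investigator or site policy. Neither has a restart rule for itching.
   - Protocol 5.5 deals with abnormal vital signs during the infusion and with reporting concerns to the blood bank. Itching is not a vital sign.
   - SAP 11.5 lists new itching and "Clinically diagnosed anaphylaxis" as separate items of the transfusion-reaction outcome. The trial's own vocabulary can therefore tell them apart, but SAP 11.5 contains no restart rule and 5.6 does not use the distinction.
   - No section says which paragraph of 5.6 prevails.

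5. **Reach of the consequence.** Under the opening paragraph, itching that clears and does not recur is not a permanent discontinuation, so the automatic label in 12.3 is not triggered. Under the second paragraph it is. In both cases final attribution belongs to the medical monitor (12.4).

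6. **Link to the analysis.** Protocol 6.1 to 6.3 list 1 primary, 11 secondary and 8 safety outcomes: 1 + 11 + 8 = 20. None of the 20 is defined by whether an infusion was restarted. The primary analysis is by randomized assignment (SAP 3). The per-protocol analysis excludes patients who failed to start their transfusion as the protocol requires (SAP 3.3), which does not turn on restarting. The transfusion-reaction outcome depends on signs within 6 hours of starting the infusion (SAP 11.5).

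**The case against.** The strongest reply is that the paragraphs carry different written labels. The first lists manifestations of transfusion reaction and the second lists signs of anaphylaxis. If each list is read under its label, simple itching is restartable, itching as part of anaphylaxis is not, and every clause has work to do, including the exemption for rash or itching. The evaluation step in the opening paragraph is a point at which the two could be told apart. This is a plausible account of what was meant, so it would go too far to say that no reconciliation exists. But the second paragraph does not make its rule depend on a diagnosis, a second sign or a severity level, so the label alone does not clearly separate isolated itching.

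A rival reading takes the second paragraph as a further restriction that overrides the first. The restart and the express exemption would then do nothing for itching. That two readings are available and lead to opposite actions is the difficulty.

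It can also be said that some variation between sites is built in, since infusion and monitoring follow site policy. That is true, but 5.6 sets its own trial-wide restart rules and does not defer to site policy on this point.

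The reply on 12.3 largely stands. Section 5.6 already requires suspected reactions that stop the transfusion to be reported as adverse events. Section 12.3 also collects non-serious events of uncertain relationship, and its Table 4 allows 72 hours for recording non-serious related events. Itching followed by a restart would ordinarily be collected too. At most, the initial relatedness label differs.

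**Conclusion.** The point holds as an internal inconsistency in a safety rule. Section 5.6 gives itching two incompatible restart instructions, and nothing in the protocol or SAP chooses between them. It should be fixed because the rule is applied at the bedside and cannot be followed consistently as written. The conclusion rests on two readings of the text: that pruritus and itching are the same symptom, and that any one listed sign is enough in each paragraph.

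The size is one symptom in one section, with a possible difference in an initial relatedness label. Some stronger readings are tempting, and the documents do not support them:

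- **Effect on outcomes.** A reader might infer that the trial's outcomes are distorted, or conversely that they cannot be affected. The documents show only that no outcome definition or analysis-set rule uses the restart decision. Stopping or restarting changes the volume received, and whether that alters any outcome cannot be judged from the text.
- **Number of patients.** No rate of itching is given, so none can be derived.
- **A second conflict for hives.** This arises only if rash in the opening paragraph is taken to include hives. The specific term can be read as governing, so it adds little.
- **Fever and heart-rate rise.** The second paragraph's catch-all could bring these in through clinical judgment, but neither that paragraph's named items nor its limits mention them in conflict with the first. They are not part of this point.

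**What to change.** The sponsor's clinical leads should reconcile the two paragraphs of Protocol 5.6 in one of two ways: put itching/pruritus under exactly one restart rule, or write out the condition that decides which paragraph applies. Which rule is right is a clinical decision and no view on it is offered here. While the section is open, a few words could say whether rash in the opening paragraph includes hives.

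The cost is a short wording clarification in 5.6, carried into any site instructions that repeat it. It needs no new procedures, data or analyses, and no change to 12.3 or the SAP.

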5.7 Plan for Plasma Shortages

In the event of a shortage of convalescent plasma or multivitamin solution for use in the trial at a participating trial site, site personnel should contact the Vanderbilt Coordinating Center (VCC) Clinical Trials Operations Manager. Participants will only be randomized when convalescent plasma and the placebo solution are available.

6. OUTCOMES

Definitions for each outcome are detailed in the trial's statistical analysis plan (SAP).

6.1 Primary Outcome

COVID-19 7-point Ordinal Clinical Progression Outcomes Scale on Study Day 15:

1. Not hospitalized with resumption of normal activities.
2. Not hospitalized, but unable to resume normal activities.
3. Hospitalized, not on supplemental oxygen.
4. Hospitalized, on supplemental oxygen.
5. Hospitalized, on nasal high-flow oxygen therapy, noninvasive mechanical ventilation, or both
6. Hospitalized, on ECMO, invasive mechanical ventilation, or both.
7. Death

6.2 Secondary Outcomes

- All-location, all-cause 14-day mortality (assessed on Study Day 15)
- All-location, all-cause 28-day mortality (assessed on Study Day 29)
- Survival through 28 days
- Time to hospital discharge through 28 days
- Time to recovery (defined as time from randomization to the earlier of final oxygen receipt in the hospital or hospital discharge)
- COVID-19 7-point Ordinal Clinical Progression Outcomes Scale on Study Day 3, 8 and 29
- Oxygen-free days through Day 28
- Ventilator-free days through Day 28
- Vasopressor-free days through Day 28
- ICU-free days through Day 28
- Hospital-free days through Day 28

6.3 Safety Outcomes

- Acute kidney injury
- Receipt of renal replacement therapy
- Documented venous thromboembolic disease (DVT or PE)
- Documented cardiovascular event (myocardial infarction or ischemic stroke)
- Transfusion reaction (fever/rash)
- Transfusion related acute lung injury (TRALI)
- Transfusion associated circulatory overload (TACO)
- Transfusion related infection

6.4 Rationale for Primary Outcome

COVID-19 has a broad spectrum of clinical severity. Even among hospitalized patients, most recover without experiencing critical illness.³⁶ Designing a trial with statistical power to detect a meaningful difference in ICU-free days or mortality might require an unfeasibly large sample size and could miss significant morbidity experienced by the majority of hospitalized patients. Since the majority of morbidity from COVID-19 relates to hypoxemia, the fact that COVID-19 Ordinal Scale is tied to degree of hypoxic respiratory failure increases its face validity and relevance. For similar reasons, previous trials of severe influenza have employed a similar ordinal outcome.³⁷ This ordinal scale has been selected as an outcome in multiple ongoing COVID-19 trials and is a preferred outcome by the World Health Organization Research and Development Blueprint for COVID-19.³⁸ Use of this standardized outcome will increase the potential to compare the results of this trial with other trials and perform meta-analyses. Validated techniques to ask questions about the resumption of normal daily activities will be used to distinguish between category 1 and category 2 on the scale.

7. DATA AND BIOLOGICAL SPECIMEN COLLECTION

Given the infectious risk from COVID-19 and potential shortages of personal protective equipment (PPE), we will minimize face-to-face contact between patients and non-clinical staff. Additionally, minimizing research activities and conducting the trial in a pragmatic manner will increase the ability to complete the trial in the face of strained clinical and research resources during the COVID-19 pandemic. We will emphasize data that can be collected from the electronic health record, and assessments that can be completed over the telephone.

Plasma samples will be collected as part of this trial at baseline (prior to study infusion) and on study Day 2 (approximately 24 hours after the study infusion. Specimens will be shipped to VUMC for future analysis, which will include quantitative anti SARS-CoV-2 antibody measurements. The study principal investigator (PI) and collaborators have approval to use all research bio-specimens collected during the conduct of this trial to address the research questions described in the consent document.

7.1 Baseline Variable Collection

- Presence or absence of each inclusion and exclusion criterion
- Date and time of randomization
- Date of symptom onset
- Admission data: date and time of presentation, origin (home, skilled nursing facility, rehabilitation/LTACH, nursing home, outside hospital, outside ICU), location at randomization [Emergency Department (ED), hospital ward, ICU]
- Demographics (age, sex, race, ethnicity, height, weight)
- Comorbidities
- Acute signs and symptoms: altered mental status, acute hypoxic respiratory failure, hematology laboratory tests, liver function tests, renal function, coagulation studies
- Sequential Organ Failure Assessment (SOFA)³³ at enrollment
- Chronic use of medications: corticosteroids, ACE inhibitors, angiotensin receptor blockers, non-steroids anti-inflammatory drugs, other
- Receipt of open label immunomodulators between hospital presentation and enrollment: corticosteroids, tocilizumab, sarilumab, interferon β , other
- Receipt of invasive mechanical ventilation, non-invasive ventilation, high-flow nasal cannula, vasopressors, and oxygen therapy between hospital presentation and enrollment
- Vital signs
- COVID-19 7-point Ordinal Clinical Progression Outcomes Scale at enrollment
- CRP, recorded if measured clinically, and collected for research if not measured clinically

7.2 Assessments Between Hospital Presentation and Hospital Discharge

- Specimen type, date, and result of SARS-CoV-2 testing conducted clinically
- Date and time of study infusion

- COVID-19 7-point Ordinal Clinical Progression Outcomes Scale on every day of hospitalization (study Day 8, 15 and 29 by phone if participant is no longer hospitalized)
- SOFA on Day 2, if hospitalized
- Receipt of open label antivirals between enrollment and hospital discharge: hydroxychloroquine, remdesivir, lopinavir/ritonavir, other
- Receipt of open label immunomodulators between enrollment and hospital discharge
- Receipt of open label COVID-19 convalescent plasma
- Date of first receipt of supplemental oxygen (if applicable)
- Date of final receipt of supplemental oxygen (if applicable)
- Date of first receipt of high flow nasal cannula (if applicable)
- Date of final receipt of high flow nasal cannula (if applicable)
- Date of first receipt of non-invasive ventilation (if applicable)
- Date of final receipt of non-invasive ventilation (if applicable)
- Date of first receipt of invasive mechanical ventilation (if applicable)
- Date of final receipt of invasive mechanical ventilation (if applicable)
- Date of first receipt of extracorporeal membrane oxygenation (if applicable)
- Date of final receipt of extracorporeal membrane oxygenation (if applicable)
- Date of first receipt of vasopressors (if applicable)
- Date of final receipt of vasopressor (if applicable)
- Date of first ICU admission (if applicable)
- Date of final ICU discharge (if applicable)
- Date of hospital discharge (if applicable)
- Date of death (if applicable)
- Clinically obtained laboratory tests, including blood counts, chemistries, and CRP
- Safety assessments: myocardial infarction, ischemic stroke, deep venous thrombosis or pulmonary embolism, aspartate aminotransferase or alanine aminotransferase levels that are greater than twice the local upper limit of normal, stage II or greater acute kidney injury according to KDIGO creatinine criteria³⁹, receipt of new renal replacement therapy, transfusion reaction, transfusion related acute lung injury (TRALI), Transfusion associated cardiac overload (TACO), transfusion related infection. Definitions for each variable are detailed in the trials statistical analysis plan and are described for enrolling personnel in the trial manual of operations and/or electronic data capture system.

